2.8.3 Vital signs, weight and physical examinations

Vital sign parameters collected are systolic and diastolic blood pressure (mmHg), pulse rate (beats per minute), body temperature (°C), and weight (kg). Vital sign values considered notably abnormal are defined in [Table 2-6](#).

Table 2-6 Criteria for notable vital sign values

Vital sign	Criteria for clinically notable vital sign values
Systolic blood pressure [mmHg]	≥180 mmHg/≤90 mmHg with increase/decrease from baseline of ≥20 mmHg

Diastolic blood pressure [mmHg]	≥105 mmHg/≤50 mmHg with increase/decrease from baseline of ≥15 mmHg
Pulse rate [bpm]	≥100 bpm/≤50 bpm with increase/decrease from baseline of >25%
Body temperature [°C]	≥ 39.1
Weight [kg]	≥10% decrease/increase from baseline

The number and percentage of patients with notable vital sign values (high/low) will be presented by treatment group.

Patients with any clinically notable vital sign value will be listed.

2.8.4 Electrocardiograms

Baseline for ECG analysis is defined as the average of all available ECG measurements associated with the baseline assessment. Scheduled study day 1 pre-dose ECGs will be considered to have been obtained prior to study drug administration if dosing time is missing.

If a patient has more than one post-baseline measurement at a specific time point, the average of all available measurements associated with the nominal time point will be used for analyses (not when flagging abnormalities).

The following summaries will be provided for each applicable ECG parameter:

- Number (%) of patients having notable ECG values according to [Table 2-7](#).

Table 2-7 Criteria for notable ECG values

ECG parameter	Criteria for notable ECG values
QT, QTcF	New absolute values >450 ms, >480 ms and >500 ms Change from baseline >30 ms and >60 ms
HR (bpm)	Increase from baseline >25% and value >100 bpm Decrease from baseline >25% and value <50 bpm
PR (ms)	Increase from baseline >25% and value >200 ms New PR >200 ms
QRS (ms)	Increase from baseline >25% and value >120 ms New QRS >120 ms

Patients with any notable change from baseline for each QT/QTc interval will be listed.

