### 7.2.2.6 Cardiac assessments (patients in PDR001 arm)

#### 7.2.2.6.1 Electrocardiogram (ECG)

A standard 12 lead ECG will be performed as per the assessment schedule in [Table 7-1](#), [Table 7-2](#), [Table 7-3](#) and [Table 7-7](#). Blood samples scheduled at the same time point should be taken after the ECGs are completed. The ECGs on Day 1 of Cycles 1 and 3 must be performed in triplicate.

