**Table 7-7 12 lead ECG collection plan for central review (patients in PDR001 arm)\*\*\***

Cycle	Day	Time
Screening/Baseline §	-28 to -1	Anytime (all patients)
1	1	*1h (±5 min) post-dose
3	1	*Pre-dose
3	1	*1h (±5 min) post-dose
Unscheduled**	-	Anytime

§ ECG at baseline should be performed for all patients.  
\* ECGs performed in triplicate.  
\*\* A PK sample should be collected just after an ECG performed due to an unexpected cardiac signal.  
\*\* Unscheduled ECGs could be performed for safety reasons for all patients.  
\*\*\* This plan is only applicable to central ECG review, which is obsolete upon implementation of Protocol Amendment 05.

All ECGs will be independently reviewed by a central laboratory. Instructions for the collection and transmission of ECGs to the central ECG laboratory will be provided in the ECG Manual.

Upon implementation of Protocol Amendment 05, the ECG collection plan for central review as detailed in [Table 7-1](#), [7-2](#), [7-3](#) and [7-7](#) is obsolete. Instead, ECGs are performed and reviewed locally, with the timing and frequency based on Investigator’s judgement.

Clinically significant abnormalities present at screening/baseline should be reported on the Medical History eCRF. New or worsened clinically significant findings occurring after informed consent must be recorded on the Adverse Events eCRF. All eligibility and patient management decisions should be made based on the local reading of the ECG.

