##### **ECG (patients in PDR001 arm)**

- Shift table screening/baseline to worst on-treatment result for overall assessments.
- Listing of ECG evaluations for patients treated with PDR001 with at least one abnormality.

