2.8 Safety analysis

Summaries and listings described in this section will be done by study treatment groups based on the Safety set:

- PDR001
- Chemotherapy
- Crossover

For crossover treatment group, summaries will be done if there are more than 10 crossover patients.

The assessment of safety is based on the type and frequency of Adverse Events (AEs) as well as on the number of laboratory values that fall outside of pre-determined ranges (Common Toxicity Criteria for Adverse Events (CTCAE) grading limits or normal ranges as appropriate). Other safety data include electrocardiogram and vital signs.

The overall observation period will be divided into three mutually exclusive segments:

- Pre-treatment period: from day of patient's informed consent to the day before first dose of study treatment,
- On-treatment period: from day of first dose of study treatment to the end of safety follow up, i.e., for PDR001, to 30 days after last dose of PDR001; For chemotherapy, to 30 days after last dose of chemotherapy.

- Post-treatment period: starting at Day 31 after last dose of PDR001 for PDR001 treatment group; Starting at Day 31 after last dose of chemotherapy for chemotherapy treatment group.

If dates are incomplete in a way that clear assignment to pre-, on-, post-treatment period cannot be made, then the respective data will be assigned to the on-treatment period.

Safety summaries will primarily be based on all data from the on-treatment period. Following last administration of PDR001, adverse events (including serious adverse events), and new antineoplastic therapies are collected for a period of 150 days. Following start of new antineoplastic therapy only treatment related adverse events will be collected. Select summaries of related adverse events will be produced for the combined on-treatment and post-treatment periods ([Section 2.8.1](#)).

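### SAP 2.8.4 tabulates notable ECG values for the Chemotherapy group, which has no scheduled post-baseline ECG, although Protocol 10.5.3.4 limits ECG outputs to the PDR001 arm

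*SAP*

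**What the plan says.** SAP 2.8 sets the layout for all safety outputs: "Summaries and listings described in this section will be done by study treatment groups based on the Safety set". The groups are PDR001, Chemotherapy and Crossover, the last only if there are more than 10 crossover patients. SAP 2.8.4 then orders the "Number (%) of patients having notable ECG values according to" Table 2-7 and names no group restriction. Elsewhere the SAP does limit groups when it means to: adverse events of special interest go to PDR001 and Crossover, the combined on- and post-treatment AE tables to PDR001, and PK to the PDR001 arm.

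The protocol is narrower. Section 10.5.3.4 heads its ECG outputs "ECG (patients in PDR001 arm", and section 7.2.2.6 on cardiac assessments carries the same restriction in its title.

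On data collection, Protocol Table 7-7 says "ECG at baseline should be performed for all patients". For patients on PDR001, section 7.2.2.6.1 adds "The ECGs on Day 1 of Cycles 1 and 3 must be performed in triplicate". The chemotherapy visit schedule (Table 7-2) marks an ECG at screening and nowhere later. Table 7-7 also notes "Unscheduled ECGs could be performed for safety reasons for all patients". Once Amendment 05 is implemented, "ECGs are performed and reviewed locally, with the timing and frequency based on" the investigator's judgement.

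SAP section 4, which is the place for changes to protocol-specified analyses, mentions only COVID-19.

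**The concern.** Every Table 2-7 criterion is either a new value or a change from baseline, so a patient can be flagged only if a post-baseline ECG exists. One group has such ECGs by plan; the other has them only if something prompts one. The denominator does not correct for this. The Safety Set needs one dose and one valid post-baseline safety assessment, and a statement of no adverse events is enough, so a patient with no post-baseline ECG is counted as free of notable values.

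A reader of the clinical study report would then see a PDR001 percentage beside a control percentage near zero, and could take the gap for a cardiac signal. The opposite error is also possible: any control ECG that does exist was probably taken for a safety reason, so a control percentage based only on those patients would come from a selected few. Neither figure is a fair comparator for scheduled ECGs on PDR001.

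**Working it through.** The documents state no figure for this output, so the check is a count of scheduled ECGs, an illustration of what that count implies, and date arithmetic for Amendment 05.

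**1. Scheduled post-baseline ECGs per patient**

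- PDR001 arm (Protocol Tables 7-1 and 7-7): Cycle 1 Day 1 at 1 h post-dose, Cycle 3 Day 1 pre-dose, Cycle 3 Day 1 at 1 h post-dose. 3 time points x 3 tracings = 9.
- Chemotherapy arm (Table 7-2): 0.
- Crossover (Table 7-3): ECGs at Cycle 1 Day 1 and Cycle 3 Day 1.

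SAP 2.8.4 averages replicates for analysis but not when flagging abnormalities, so one tracing out of a triplicate can flag a PDR001 patient.

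**2. Group sizes.** The Amendment 05 study status gives 122 randomised, 82 to PDR001. Control arm: 122 - 82 = 40.

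**3. What unequal ascertainment alone produces.** Assume the same chance p of a notable value per ECG in both arms, independence, and all 82 PDR001 patients completing the schedule. The probability that a patient is flagged at least once in k ECGs is 1 - (1 - p)^k. Use k = 3 if the replicates in a triplicate always agree, and k = 9 if they are independent; the truth should lie between.

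| p per ECG | PDR001, k = 3 | PDR001, k = 9 | Expected of 82 | Control, scheduled ECGs |
|---|---|---|---|---|
| 0.5% | 1.5% | 4.4% | 1.2 to 3.6 | 0 of 40 |
| 1% | 3.0% | 8.6% | 2.4 to 7.1 | 0 of 40 |
| 2% | 5.9% | 16.6% | 4.8 to 13.6 | 0 of 40 |
| 5% | 14.3% | 37.0% | 11.7 to 30.3 | 0 of 40 |

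For example, at p = 1%: 1 - 0.99^3 = 0.030 and 1 - 0.99^9 = 0.086. The values of p are assumptions; the documents give none. Because p is equal in the two arms, all of the gap is ascertainment.

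**4. Reach of Amendment 05 (30 Aug 2018).** The last first dose was on 3 Aug 2018, so every PDR001-arm Cycle 1 Day 1 ECG predates the amendment. Nominal Cycle 3 Day 1 is first dose + 56 days. By 16 Oct 2017, 76 of the 82 PDR001-arm patients were randomised (Amendment 04 study status). Allowing 3 days to first dose, their Cycle 3 Day 1 fell no later than about 16 Oct 2017 + 59 days = 14 Dec 2017. At most 82 - 76 = 6 of 82 (7.3%) could have had a scheduled Cycle 3 Day 1 ECG fall after the amendment, barring long dose delays. No ECG is scheduled after Cycle 3 Day 1.

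**The case against.** The strongest reply is that this is a descriptive count. No ECG test is specified, and Protocol 10.5.3.4 treats any safety test as exploratory. The column layout and denominators may also be settled in the TFL shells, which are a separate document. The first part stands and limits the weight of the point. The second cannot be checked, and the SAP should not depend on the shells to correct a rule that it states itself.

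Three stronger readings are tempting, and the documents do not support them.

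- **That the control percentage must be zero, so the comparison is fixed by the schedule.** Unscheduled safety ECGs are allowed for all patients, so a control patient can be flagged. Ascertainment is unequal, not absent.
- **That the SAP pools centrally read and local ECGs.** It has no rule on ECG source. Protocol 9.3 speaks of central processing, 7.2.2.6.1 sends new clinically significant findings to the adverse event form, and nothing shows that local interval measurements reach the ECG dataset. Pooling would be an inference from silence.
- **That the 18 PDR001 and 4 crossover patients on treatment at 10 Aug 2018 lost planned ECGs through Amendment 05.** In the PDR001 arm the bound is about 6 of 82. Crossover start dates are not given, and that group is summarised only above 10 patients.

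It is also fair to object to a remedy that simply moves local ECGs to the existing listing. The only listing in SAP 2.8.4 covers notable QT/QTc change, so notable heart rate, PR and QRS values from those ECGs would appear in no ECG output.

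**Conclusion.** The point holds as a mismatch between SAP 2.8.4, the protocol's stated scope and the data collected. Followed as written, the SAP adds a Chemotherapy column that the protocol does not call for, fills it from an arm with no planned post-baseline ECG, and does not record the change. The contrast is then up to 9 scheduled tracings against 0. Under the illustrative 1% rate that is an apparent excess of roughly 3 to 9 percentage points on PDR001 with no drug effect; the size scales with the assumed rate and would shrink if controls had unscheduled ECGs or PDR001 patients missed scheduled ones.

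The consequence is a misleading descriptive safety table. No efficacy result, hypothesis test or patient procedure is affected. The conclusion rests on reading the SAP 2.8 group rule as applying to 2.8.4, which is what the text says, and on the absence of any ECG-specific denominator.

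**What to change.** In SAP 2.8.4:

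1. Restrict the notable-ECG table to PDR001-treated patients: the PDR001 arm, with Crossover shown separately if that group is summarised.
2. Use as denominator the patients with a baseline and at least one post-baseline ECG, and print that number.
3. Extend the listing to every notable unscheduled or local ECG for QT/QTc, heart rate, PR and QRS, in all three groups, flagged by source (scheduled central, unscheduled, or local after Amendment 05). Notable control ECGs then remain visible without being turned into a rate.

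If the sponsor prefers to keep the Chemotherapy column, SAP section 4 should declare it as a change from Protocol 10.5.3.4, and the table should show the number with a post-baseline ECG in each group and carry a footnote that the control arm had none scheduled.

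The cost is a few lines of SAP text, one removed column and a slightly wider listing. No new data are needed.

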2.8.5 Tolerability

Tolerability of study treatment will be assessed by summarizing the number of dose interruptions by study treatment. Reasons for dose interruption will be listed by patient and study treatment and summarized by study treatment. Cumulative dose, dose intensity and relative dose intensity of study treatment (see Section 2.5.1) will be also be used to assess tolerability.

2.9 Pharmacokinetic data

All PK analyses will be performed based on the PAS for PDR001 arm. Patient data may be removed on an individual basis. PK parameters will be calculated using noncompartmental methods and summarized as described in [Table 2-8](#). The PK parameters considered primary are AUCinf, AUCtau (AUC0-672h), AUClast, Cmax, and Tmax. Other PK parameters (CL, Vz, T1/2) are considered as secondary. All primary PK parameters will be summarized and all PK parameters will be listed.

The descriptive statistics of all pharmacokinetic parameters in the [Table 2-8](#) for both Cycle 1 and Cycle 3 will include arithmetic and geometric mean, median, SD, and CV, geometric CV, minimum and maximum.

Summary statistics will be presented for PDR001 serum concentrations at each scheduled time point. Descriptive graphical plots of individual serum concentration versus time profiles and mean concentration versus time profiles will be generated by cycle.

Table 2-8 PK parameters – descriptive statistics

Parameters	Descriptive statistics
AUCinf, AUCtau (AUC0-672h), AUClast, Cmax, Tmax, T1/2, Racc, CL, Vz, Clast, Tlast	Mean, standard deviation, CV% mean, geometric mean, CV% geometric mean, median, minimum and maximum
CV% = coefficient of variation (%) = sd/mean*100	
CV% geometric mean = sqrt (exp (variance for log transformed data)-1)*100	

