## **Amendment 03 (27-Jul-2016)**

### **Amendment rationale**

With the available PK data obtained from the single agent first-in-human study CPDR001X2101, an exploratory population PK (PopPK) analysis showed that the T1/2 of PDR001 in man is 20 [17, 23] days (mean [90% CI]). Using five times the upper limit of the half-life of 23 days and an added safety margin, the protocol is amended to increase the duration of contraception and safety follow-up period post PDR001 treatment from 90 days to 150 days. These changes are related to an Urgent Safety Measure communicated on 08-Jun-2016 to all investigators.

This amendment also introduces the following changes.

Clarification of Inclusion Criterion 8: specify that lesions in previously irradiated areas should not be considered measurable unless there is clear evidence of progression in such lesions since the radiotherapy.

Modification of Exclusion Criterion 8: Patients who have previously received an investigational therapeutic cancer vaccine can be eligible. This change has been introduced considering the limited efficacy evidence available for cancer vaccines and the high unmet medical need in this patient population.

Clarification of Exclusion Criterion 10: Patients who have previously received an investigational therapeutic cancer vaccine are eligible providing there is a minimum 4-week washout period between the last dose of the vaccine and the first dose of PDR001.

The ECG monitoring plan is simplified to collection of ECGs at screening, Cycle 1 day 1, Cycle 3 day 1 and as clinically indicated, because no signal of QT interval prolongation was observed in the first in human study (CPDR001X2101) (see PDR001 Investigator's Brochure) or other currently approved anti-PD-1 antibodies (see KEYTRUDA® and OPDIVO® labels).

There is a clerical error in the previous version of the protocol within the criteria for discontinuation language in Section 7.1.3 (Discontinuation of study treatment). Amendment 2 equivocally indicated that patients must be discontinued from treatment upon observance of any of the events listed in the section. This section has been clarified by differentiating reasons that may cause treatment discontinuation from those that require mandatory treatment discontinuation.

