#### 6.1.2 Treatment duration

All patients treated with either PDR001 or chemotherapy (per Investigator's choice) will begin treatment on Cycle 1 Day 1. Each cycle will have 28 days if treated with PDR001. Patients may be discontinued from study treatment earlier due to unacceptable toxicities, confirmed disease progression (per irRC only for patients treated with PDR001) and/or treatment is discontinued at the discretion of the investigator or the patient. Patients who discontinue study treatment should not be considered discontinued from the study (please refer to [Section 7.1.3](#) and [Section 4.3](#) for further details).

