**Table 10-1 Noncompartmental pharmacokinetic parameters**

AUClast	The AUC from time zero to the last measurable concentration sampling time (tlast) (mass x time x volume  )
AUCinf	The AUC from time zero to infinity (mass x time x volume  )
AUCtau	The AUC calculated to the end of a dosing interval (tau) at steady-state (amount x time x volume  )
Cmax	The maximum (peak) observed plasma, blood, serum, or other body fluid drug concentration after single dose administration (mass x volume  )
Tmax	The time to reach maximum (peak) plasma, blood, serum, or other body fluid drug concentration after single dose administration (time)
T1/2	The elimination half-life associated with the terminal slope ( $\lambda_z$ ) of a semi logarithmic concentration-time curve (time). Use qualifier for other half-lives
CL	The total body clearance of drug from the plasma (volume x time  )
Vz	The apparent volume of distribution during terminal phase (associated with $\lambda_z$ ) (volume)

PAS will be used in all pharmacokinetic data analysis and PK summary statistics, as appropriate.

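### SAP 2.9 summarises AUCinf for Cycle 3 as well as Cycle 1, although the Cycle 3 value carries over earlier doses and about 38% of the Cycle 1 value is extrapolated

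*SAP*

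**What the plan says.** SAP 2.9 ranks the parameters in two tiers. For the first: "The PK parameters considered primary are AUCinf, AUCtau (AUC0-672h), AUClast, Cmax, and Tmax". For the second: "Other PK parameters (CL, Vz, T1/2) are considered as secondary". It then says "All primary PK parameters will be summarized and all PK parameters will be listed". The next paragraph opens with "The descriptive statistics of all pharmacokinetic parameters in the", refers to Table 2-8, and extends those statistics to both Cycle 1 and Cycle 3. Table 2-8 lists "AUCinf, AUCtau (AUC0-672h), AUClast, Cmax, Tmax, T1/2, Racc, CL, Vz, Clast, Tlast" with no restriction by cycle.

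The protocol is looser. Section 10.5.4 treats the parameters as ones that may be assessed and reports them where feasible. Table 10-1 defines AUCinf as "The AUC from time zero to infinity" without tying it to a first dose, ties AUCtau to a dosing interval at steady state, and describes CL in words without a formula. Section 7.2.3 names Cycles 1 and 3 only for the AUC to the last measurable sample, and its parameter list includes neither AUCinf nor CL.

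On timing, Protocol 6.1.2 says "Each cycle will have 28 days if treated with PDR001". Table 7-8 ends the Cycle 1 and Cycle 3 profiles at 672 h (±48 h), just before the next dose. The only half-life given is in the Amendment 03 rationale, where the value "of PDR001 in man is 20 [17, 23] days (mean [90% CI" comes from an exploratory population PK analysis of the first-in-human study.

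Neither document asks for the extrapolated share of AUCinf to be reported, and neither sets a limit on it.

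**The concern.** AUCinf is the area to the last sample plus a tail projected from the terminal slope. Two separate problems follow.

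- **Cycle 1.** The profile stops after 28/20 = 1.4 half-lives, so a large part of AUCinf is projection.
- **Cycle 3.** The curve starts with drug left over from two earlier doses. The area from the third dose to infinity therefore exceeds what a single dose produces, whether or not the pharmacokinetics have changed.

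Characterising the PK profile is a stated secondary objective. A table showing AUCinf by cycle invites the reader to see a rise in exposure or a fall in clearance over time where there may be none.

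**Working it through.** The documents give no extrapolated share or bias figure to reproduce. One check passes: 28 days × 24 = 672 h, which matches the AUCtau interval in the SAP.

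**Inputs.** Dosing interval 28 days (Protocol 6.1.2). Last sample at 672 h (Table 7-8). Half-life 20 days, range 17 to 23 (Amendment 03 rationale). Assumption: linear, one-compartment kinetics, so that doses superpose.

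**Formulas.** Let r = 2^(−28/half-life), the fraction remaining after one interval.

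| Quantity | Formula | 17 d | 20 d | 23 d |
|---|---|---|---|---|
| Fraction remaining | r | 0.319 | 0.379 | 0.430 |
| Share of Cycle 1 AUCinf beyond 672 h | r | 31.9% | 37.9% | 43.0% |
| Cycle 3 AUCinf ÷ single-dose AUCinf | 1 + r + r² | 1.42 | 1.52 | 1.62 |
| Cycle 3 CL error if Dose/AUCinf | 1/(1 + r + r²) − 1 | −30% | −34% | −38% |
| Cycle 3 AUCtau ÷ single-dose AUCinf (fraction of steady state) | (1 − r)(1 + r + r²) = 1 − r³ | 0.967 | 0.946 | 0.920 |
| Cycle 3 CL error if Dose/AUCtau | 1/(1 − r³) − 1 | +3% | +6% | +9% |

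At 20 days: r = 2^(−1.4) = 0.379; 1 + 0.379 + 0.144 = 1.523; 1/1.523 = 0.657, that is 34% too low.

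**Sampling window.** With the last sample at 26 or 30 days in place of 28, the extrapolated share at a 20-day half-life is 40.6% or 35.4%.

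**Terminal slope.** The last three samples (168, 336 and 672 h) span 504 h = 21 days, or 21/20 = 1.05 half-lives (0.91 to 1.24). The slope that carries the extrapolation is itself weakly determined.

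**Two-compartment sensitivity (assumption, not in the documents).** Let a fast phase with a 2-day half-life carry a fraction w of AUCinf, with w up to 0.20. Its contribution beyond 28 days is negligible (2^(−14)).

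- The extrapolated share becomes about (1 − w)r. At w = 0.20 it is 25.5%, 30.3% and 34.4% for 17, 20 and 23 days.
- The Cycle 3 ratio becomes w + (1 − w)(1 + r + r²). At w = 0.20 it is 1.34, 1.42 and 1.49.
- Across w from 0 to 0.20 and half-lives of 17 to 23 days, the ranges are about 25 to 43% extrapolated, a Cycle 3 ratio of 1.34 to 1.62, and a Dose/AUCinf clearance 25 to 38% too low.

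**What the 1.52 means.** In the one-compartment case the ratio of Cycle 3 to Cycle 1 AUCtau is also 1 + r + r². There it is the accumulation ratio, and a reader expects it. In AUCinf the same factor looks like a change in the drug's disposition.

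**The case against.** The strongest reply has four parts.

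1. **Clearance.** A reader might infer that following the SAP will produce a Cycle 3 clearance about 34% below Cycle 1. The documents do not support that. No CL formula is given. AUCtau is already a primary parameter, and Dose/AUCtau would err by only about 6% in the other direction. One sentence of SAP 2.9 also implies that CL and Vz, being secondary, are only listed. This objection stands: the clearance figure is conditional, and for CL and Vz the defects are an unstated formula and an internal contradiction. AUCinf is untouched by it, because as a primary parameter it is summarised on either reading.
2. **Discretion.** The protocol reports parameters where feasible, and the SAP allows individual patients' data to be removed. An unreliable AUCinf can therefore be left out. That is true, but the stated ground for removal is the number of samples. It does not reach Cycle 3 carry-over, which occurs in a fully sampled patient.
3. **Half-life.** It is an exploratory estimate from another study, reported in an amendment rationale. The direction and rough size nevertheless hold across 17 to 23 days and with the assumed fast phase.
4. **Consequence.** Because AUCinf is labelled primary, a reader might suppose that trial conclusions depend on it. They do not. The label ranks parameters within a descriptive secondary objective, and the non-extrapolated measures (AUCtau, AUClast, Cmax, Tmax) are summarised in any case.

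**Conclusion.** The point holds for AUCinf. The SAP's instruction to summarise it in both cycles gives a Cycle 3 value about 1.5 times the single-dose value (1.42 to 1.62; 1.34 to 1.62 with the assumed fast phase) through carry-over alone. The Cycle 1 value is about 38% extrapolated (32 to 43%; about 25 to 43% with the fast phase). Carry-over affects Cycle 3 only. In Cycle 1 the problem is extrapolation, which makes the value uncertain but does not by itself bias it.

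For clearance the conclusion is conditional: about 34% too low (30 to 38%) in Cycle 3 if Dose/AUCinf is used. Which formula applies, and whether CL and Vz are summarised at all, cannot be settled from the documents.

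The figures assume linear kinetics and the 17 to 23 day half-life. The matter is minor: no hypothesis, decision rule, alpha or sample size uses these parameters, and PFS is unaffected.

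**What to change.** Amend SAP 2.9 and Table 2-8 as follows.

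- Restrict AUCinf, and any CL or Vz derived from it, to Cycle 1, and report the extrapolated percentage beside it.
- Use AUCtau for Cycle 3 exposure and for the comparison of Cycle 1 with Cycle 3, read as accumulation.
- State Cycle 3 CL as Dose/AUCtau, with a note that it is about 6% too high (3 to 9%) because Cycle 3 is at about 92 to 97% of steady state.
- Reconcile the sentence that summarises primary parameters and lists all of them with the one that gives statistics for every Table 2-8 parameter.

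A cut-off on the extrapolated share is not proposed. With a typical profile at about 38%, any limit clearly below the 32 to 43% range would remove most Cycle 1 AUCinf values. Showing the percentage lets the reader judge.

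The cost is a wording change with no new data. The downside is that no Cycle 3 AUCinf is reported.
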